Investigator-Initiated Study Protocol

A **R**andomized, **C**ontrolled, **M**asked (Reading Center) **P**rospective **S**tudy of the **E**ffectiveness and **S**afety of the Ocular **T**herapeutix Dextenza (dexamethasone **O**phthalmic insert) 0.4 mg for the treatment of post-operative inflammation and pain in patients who have undergone **P**hotorefractive **K**eratectomy (PRK)

The **R**ESTORE Study

Compound:

DEXTENZA (dexamethasone ophthalmic insert) 0.4 mg for intracanalicular use

Study Name:

A Randomized, Controlled, Masked (Reading Center) Prospective Study of the Effectiveness and Safety of the Ocular Therapeutix Dextenza (dexamethasone ophthalmic insert) 0.4 mg for the treatment of post-operative inflammation and pain in patients who have undergone Photorefractive Keratectomy (PRK)-The RESTORE Study

Clinical Phase:

Prospective, Randomized, Controlled, Masked Investigator-Initiated Trial

Date of Issue:

December 17, 2019

Primary Investigator:

[name]

Sub Investigator:

[name]

Site Name & Location:

Vance Thompson Vision Center
[name]
Sioux Falls, South Dakota
57108

CLINICAL STUDY PROTOCOL SYNOPSIS

TITLE	A Randomized, Controlled, Masked (Reading Center) Prospective Study of the Effectiveness and Safety of the Ocular Therapeutix Dextenza (dexamethasone ophthalmic insert) 0.4 mg for the treatment of post-operative inflammation and pain in patients who have undergone Photorefractive Keratectomy (PRK)
SITE LOCATION(S)	Vance Thompson Vision Center [name]
PRINCIPAL INVESTIGATOR	[name]
OBJECTIVE(S)	To determine patient preference and treatment outcomes with an intracanalicular dexamethasone (0.4mg) insert compared to standard steroid drop regimen in the contralateral eye following bilateral PRK surgery.
STUDY DESIGN	Prospective Open-label Interventional Study Randomized, self-controlled design in which one eye (Group A) receives Dextenza and the second eye (Group B) receives prednisolone acetate 1% QID 1 week, BID 1 week following bilateral PRK surgery. All eyes will receive topical moxifloxacin QID for one week. Moxifloxacin is used post-op regardless of the research. Post-operative evaluations to be performed on Day 3 and Day 4, Month 1, and Month 3. Phone call survey to be performed on Week 2.
STUDY DURATION	3 months
ESTIMATED STUDY COMPLETION DATE	January 2021
POPULATION	
Sample Size:	N=20 (40 eyes)
Target Population:	Patients planning to undergo bilateral Photorefractive Keratectomy (PRK) surgery.
TREATMENT(S)	

Study Drug	DEXTENZA (dexamethasone ophthalmic insert) 0.4 mg for intracanalicular use
Dose/Route/Schedule:	All patients will be enrolled for bilateral PRK surgery. The first eye will be randomized to Group A or B; the second eye will be selected for the opposite group. Group A will receive Dextenza at the time of PRK surgery while Group B will receive prednisolone acetate 1% QID 1 week, BID 1 week following bilateral PRK surgery. All eyes will receive topical moxifloxacin QID for 1 week. Moxifloxacin is used post-op regardless of the research.
ENDPOINT(s)	
Primary:	Adapted COMTOL Survey
Secondary:	Percentage of eyes epithelialized at POD 4 Corneal Staining Corneal haze Ocular Pain Assessment Uncorrected distance visual acuity Corrected distance visual acuity Manifest refraction spherical equivalent Modified SPEED questionnaire
Safety:	IOP spikes (increase of 10 mm Hg or greater than baseline) Adverse events

TABLE OF CONTENTS

Clinical Study Protocol Synopsis	2
List of Tables	5
1. Introduction and Rationale	6
1.1 Introduction	6
1.2 Rationale.....	6
1.2.1 Rationale for Study Design	7
2. Study endpoints	7
2.1 Primary Endpoint.....	7
2.2 Secondary Endpoints	7
2.3 Safety Endpoints.....	8
3. Study Design.....	8
3.1 Study Description and Duration	8
4. Selection, Withdrawal, and Replacement of Patients.....	8
4.1 Study Population	8
4.1.1 Inclusion Criteria.....	8
4.1.2 Exclusion Criteria.....	9
4.2 Treatment Logistics and Accountability	9
4.2.1 Packaging, Labeling, and Storage	9
4.2.2 Supply and Disposition of Treatments	10
4.2.3 Treatment Accountability.....	10
4.3 Concomitant Medications and Procedures	10
5. Study Schedule of Events and Visit Descriptions	10
5.1 Schedule of Events	10
5.2 Study Visit Descriptions	11
5.2.1 Study Procedures.....	11
5.2.2 Unscheduled Visits.....	14
5.2.3 Adverse Event Information Collection.....	14
5.3 Rescue Criteria.....	15
6. Safety Definitions, Reporting, and Monitoring.....	15
6.1 Definitions	15
6.1.1 Adverse Event	15

6.1.2	Serious Adverse Event	15
6.2	Recording and Reporting Adverse Events	16
7.	Study Variables.....	16
7.1	Demographic and Baseline Characteristics	16
8.	Ethical and Regulatory Considerations.....	16
8.1	Good Clinical Practice Statement.....	16
8.2	Informed Consent	16
8.3	Patient Confidentiality and Data Protection	17
8.4	Institutional Review Board	17

LIST OF TABLES

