3. STUDY DESIGN

3.1 Study Description and Duration

This prospective, open-label, single-center, randomized, investigator-sponsored clinical study seeks to investigate the outcomes of patients undergoing bilateral PRK surgery with the treatment of a dexamethasone intracanalicular insert compared to topical standard of care steroid. All eyes will receive treatment. Additionally, all eyes will receive topical moxifloxacin QID for 1 week. Moxifloxacin is used post-op regardless of the research.

Twenty patient eyes undergoing bilateral PRK surgery will be randomized to receive either Dextenza (Group A) OR standard of care prednisolone acetate 1% QID for 1 week, BID for 1 week (Group B). The contralateral eye will receive treatment with either Dextenza or topical prednisolone as a comparator based on randomization of first eye to Group A or Group B. Post-operative evaluations to be performed on Day 3, Day 4, phone call survey at Week 2, Month 1, and Month 3.

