4.1.2 Exclusion Criteria

A patient who meets any of the following criteria will be excluded from the study:

- Patients under the age of 18.
- Patients who are pregnant (must be ruled out in women of child-bearing age with pregnancy test).
- Active infectious ocular or systemic disease.
- Patients with active infectious ocular or extraocular disease.
- Patients actively treated with local or systemic immunosuppression including systemic corticosteroids.
- Patients with known hypersensitivity to Dexamethasone.
- Patients with severe disease that warrants critical attention, deemed unsafe for the study by the investigator.
- Patients with a history of ocular inflammation or macular edema.
- Patients with allergy or inability to receive intracameral antibiotic.
- Patients on systemic non-steroidal anti-inflammatory drugs (NSAID) greater than 1,200 mg/day
- Patients with a corticosteroid implant (i.e. Ozurdex).
- Patient with corneal pathology which pre-disposes them to unsatisfactory outcomes.
- Patients who do not have 20/20 snellen visual acuity potential pre-operatively.
- MRSE greater than 6 diopters.
- Greater than 2 diopters anisometropia.

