5.2 Study Visit Descriptions

5.2.1 Study Procedures

Visit 1: Screening/Baseline (Day -30 to -1)

After the patient has provided informed consent, the following information will be collected:

- Inclusion/exclusion

- Demographics
- Medical History and Concurrent Illnesses
- Concomitant Medications
- Randomization
- Uncorrected Distance visual acuity as measured by ETDRS chart at 4m
- Manifest Refraction
- Best-corrected visual acuity as measured by ETDRS chart at 4m
- Corneal haze (via AS-OCT)
- Intraocular pressure
- Corneal Staining
- Slit Lamp Exam
- Ophthalmic Examination (dilated fundus exam)
- Subject reported AEs prior to or after surgery
- Ocular pain assessment
- Modified Speed questionnaire

Visit 2: Surgical Day 0

- Concomitant medications
- Confirm treatment group
- Record any surgical complications
- Subject reported AEs prior to or after surgery
- Intracanalicular dexamethasone insert
- Prescribe post-operative topical therapy regimen

Visit 3: Day 3

- Concomitant medications
- Intraocular pressure
- Corneal staining
- Slit lamp exam
- Subject reported AEs prior to or after surgery
- Insert visualization
- Ocular pain assessment

Visit 4: Day 4

- Concomitant medications
- Intraocular pressure
- Corneal staining
- Slit lamp exam
- Subject reported AEs prior to or after surgery
- Insert visualization
- Ocular pain assessment

Phone Call 1: Day 14 (+/- 2 days)

- Subject reported AEs prior to or after surgery
- Ocular pain assessment

Visit 5: Day 28 (+/- 3 days)

- Concomitant medications
- Uncorrected Distance visual acuity as measured by ETDRS chart at 4m
- Best-corrected visual acuity as measured by ETDRS chart at 4m
- Manifest refraction
- Corneal haze
- Intraocular pressure
- Corneal staining
- Slit lamp exam
- Subject reported AEs prior to or after surgery
- Insert visualization
- Ocular pain assessment
- Modified Speed questionnaire
- Adapted COMTOL Survey

Visit 6: Month 3 (+/- 3 days)

- Concomitant medications
- Uncorrected Distance visual acuity as measured by ETDRS chart at 4m
- Best-corrected visual acuity as measured by ETDRS chart at 4m
- Manifest refraction
- Corneal haze
- Intraocular pressure
- Corneal staining
- Slit lamp exam
- Subject reported AEs prior to or after surgery
- Insert visualization

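### The protocol randomizes an undefined first eye at screening, up to 30 days before surgery, so in this open-label trial the choice of which eye gets the insert is open to steering

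*Protocol*

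**What the plan says.** The synopsis (Treatment(s), Dose/Route/Schedule) gives the rule: "The first eye will be randomized to Group A or B; the second eye will be selected for the opposite group". Section 3.1 repeats it for the fellow eye, whose treatment is "based on randomization of first eye to Group A or Group B". The study-design row of the synopsis words it differently: "one eye (Group A) receives Dextenza and the second eye (Group B) receives prednisolone acetate 1"%, which read literally always puts the second eye in Group B.

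On timing, Table 1 marks randomization only in the Screening/Baseline column. Section 5.2.1 lists it under "Visit 1: Screening/Baseline (Day -30 to -1"). The only allocation step at the surgical visit is "Confirm treatment group". There is one surgical visit, Day 0, for both eyes.

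The synopsis and section 3.1 call the study open-label. Section 5.2.1 provides a masked examiner for slit lamp and corneal staining. Section 4.1.2 excludes "Greater than 2 diopters anisometropia", so eligible eyes may differ by up to 2 D.

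**The concern.** In a contralateral-eye trial each patient is their own control, and the one thing left to chance is which eye gets which treatment. That protects the comparison only if the identity of the randomized eye is fixed before the group is known, by a rule nobody can bend.

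Here the group is known from screening, but the eye it applies to is not defined. On one natural reading, the first eye is the first to be operated on. Someone who knows that the first eye is to receive the insert could then place it in either eye by choosing which to treat first. An eye expected to heal more easily, with less correction to make or a better surface, could go to the favoured product without breaking any written rule.

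The outcomes most exposed are the patient-reported ones: preference on the adapted COMTOL survey (primary) and the pain score per eye. Masked slit-lamp and staining examinations protect the reading of those signs, not the assignment of eyes.

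**Working it through.** **Step 1: the allocation passages side by side.**

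| Place | Eye randomized | Is that eye identified? |
|---|---|---|
| Synopsis, Dose/Route/Schedule | first eye, to A or B | no |
| Section 3.1 | first eye, to A or B | no |
| Synopsis, Study Design | one eye is A, the second eye is B | no, and the second eye is tied to B |
| Table 1 footnotes | refer to the eye assigned to A | no |

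No row names the right or left eye, the dominant eye or the order of surgery.

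**Step 2: timing.** Randomization falls in the window Day -30 to -1 and surgery on Day 0. The group is therefore known between 1 and 30 days before the first step that needs it. Both such steps, placing the insert and prescribing the topical regimen, are marked at Day 0 in Table 1.

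**Step 3: list order at Visit 1.** Inclusion/exclusion is the first item and randomization the fifth. Uncorrected acuity, refraction, best-corrected acuity, haze, pressure, staining, pain and the SPEED questionnaire follow. Some of these decide eligibility: refraction settles "MRSE greater than 6 diopters" and the anisometropia limit, and acuity settles the 20/20 potential. But the list is introduced only with "After the patient has provided informed consent, the following information will be collected", which states no sequence. Table 1 also puts inclusion/exclusion above informed consent, so its rows cannot be read as a strict time order.

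**Step 4: scale.** The protocol gives no figure for this point. Its sample size is consistent (20 patients x 2 eyes = 40 eyes). Everything below rests on assumed inputs.

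*Baseline gap in dioptres.* Expected A-B gap = share of patients steered x mean absolute difference between eyes. With assumed shares of 25% to 50% and assumed differences of 0.5 to 1.0 D:
- 0.25 x 0.5 = 0.125 D
- 0.5 x 1.0 = 0.5 D

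With no steering the expected gap is 0.

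*Effect on a paired test.* Take 20 pairs, no true treatment effect, and a two-sided 5% paired t-test on a per-eye outcome. In a share f of patients the eye with the better prognosis goes to the insert. Let rho be the correlation between the prognostic difference and the outcome difference, both standardized and normal. Then bias = rho x f x 0.798, in SDs of the paired difference, where 0.798 is the mean absolute value of a standard normal. For rho = 0.5 and f = 0.5 this is 0.5 x 0.5 x 0.798 = 0.20. Type I error by simulation, 40,000 runs per setting:

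| f | rho 0.3 | rho 0.5 | rho 0.8 |
|---|---|---|---|
| 0.10 | 5.0% | 5.3% | 5.9% |
| 0.25 | 5.8% | 7.1% | 11.0% |
| 0.50 | 8.4% | 14.1% | 31.2% |
| 1.00 | 18.2% | 45.4% | 95.0% |

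At f = 0 the test is exact at 5%; the simulated values were 4.8% to 5.5%. At f = 0.50 the bias is 0.12, 0.20 and 0.32 SD across the three columns.

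**The case against.** The steering route is an inference. No passage says that Visit 1 yields only a group label with the eye to be named later. What is randomized is an eye, Day 0 merely confirms the group, and the Table 1 footnotes treat each eye as already assigned. If the eye is named at Visit 1 by a fixed rule, surgical order changes nothing. Such a rule, and the means of concealment, could sit in a randomization plan that is not shown. Randomizing before the day of surgery is not a fault in itself. The literal clash over the second eye being Group B probably means no more than the other eye.

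Much of this stands. The missing concealment detail is not counted here, early randomization alone is not criticized, and the Group B wording is minor. What the objection does not remove is that the protocol itself states the unit and the time of randomization, and states the unit so that two readings are open. One of them leaves the assignment of eyes to be settled after the group is known.

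A reader might also infer from the Visit 1 list that patients are randomized before eligibility is established. The documents do not support that: inclusion/exclusion comes before randomization in both the list and Table 1. Randomization is listed only before the ocular measures, and list order is not stated to be time order.

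**Conclusion.** The point holds as a weakness of design: an undefined first eye combined with allocation known up to 30 days ahead in an open-label trial. Neither element alone would carry it.

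Its size cannot be derived from the documents. The dioptre gap and the error rates rest wholly on assumed shares, differences and correlations; the only documented figure is the 2 D limit. The protocol names no test, and the paired t-test stands for a per-eye outcome such as pain, not for the preference endpoint. On those terms, steering matters only if it is frequent or if the eyes differ in a way that affects outcome, and the documents show neither.

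Two stronger conclusions are tempting. One is that eyes will be steered; the protocol only leaves it possible. The other is that steering could never be detected. Refraction, acuity, haze, pressure, staining and pain are all recorded at Visit 1, so the groups can be compared on them. That check is partial: 20 pairs give it limited power, and it misses any reason for choosing an eye that was not recorded.

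**What to change.** 1. In the synopsis and section 3.1, randomize a fixed eye. For example, the right eye is randomized to Group A or B and the left eye takes the other group. Surgical order then has no bearing on allocation.
2. In Table 1 and section 5.2.1, move randomization from Visit 1 to Visit 2 (Day 0), and state that allocation is revealed only after eligibility and all baseline scores are recorded.
3. In the study-design row of the synopsis, reword the phrase that ties the second eye to Group B so that it agrees with the allocation rule.

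The cost is a few words and one mark moved in Table 1. Every patient receives exactly one insert whichever eye is chosen, so supply does not depend on early allocation. No visit, procedure or patient is added, and no clinical management changes.

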1. INTRODUCTION AND RATIONALE

1.1 Introduction

Photorefractive Keratectomy (PRK) is a well-studied, FDA approved, refractive surgery option for many patients. Post-operatively patients are commonly treated with antibiotic drops for infection prophylaxis, steroid drops for inflammation and corneal haze prevention, and finally NSAIDs (non-steroidal anti-inflammatory drugs) for pain management. Although the types of medications are standardized, there are many different protocols that vary based on surgeon and practice preference.

Post-operative drop regimens frequently induce both concerns and questions for patients undergoing ocular surgery. Poor compliance with post-operative medications can lead to unexpected and or unsatisfactory outcomes. With refractive surgery visual outcomes and safety at such a high level, patient satisfaction and experience can be altered by post-operative convenience.

Dextenza (dexamethasone 0.4mg ophthalmic insert) is a steroid eluting intracanalicular plug approved on-label for the treatment of pain and post-operative inflammation in patients who've undergone ocular surgery. Utilizing Dextenza, in place of ophthalmic steroid drops, will provide patients with a lessened number of post-operative drops which decreases both contamination possibilities and improper drug installation. Dextenza's hydrogel technology is proposed to offer patients a gradual sustained delivery of steroid to the ocular surface which may decrease subjective post-operative pain.

The tear film is a key component in corneal epithelial healing as well as refractive outcomes in PRK. In many studies, inflammation and inflammation markers are a driver to decreasing tear film homeostasis. With an intracanalicular steroid plug there is potential benefit to restoring tear film homeostasis sooner, combined with increased tear volume, leading to improved epithelialization and refractive outcomes. Finally, intracanalicular steroid plugs offer patients a preservative free steroid option to further promote epithelial health by decreasing topical preservatives.

1.2 Rationale

DEXTENZA (dexamethasone 0.4mg ophthalmic insert) has increasing research and evidence for post-cataract surgery patients, but a gap remains in many other ophthalmic surgeries. Refractive surgery, similar to cataract surgery, has post-operative visual acuity as a major determinant of surgery success. Dextenza's ability to treat post-operative inflammation while also increasing remaining tear volume by punctal occlusion has potential to improve visual outcomes for patients while also decreasing post-operative drop inconvenience.

1.2.1 Rationale for Study Design

This prospective contralateral eye study will compare the outcomes of 20 patients undergoing bilateral PRK. In one eye the patient will receive a topical steroid and the contralateral eye will receive a Dextenza ophthalmic insert. Both eyes will receive a topical antibiotic.

The primary endpoint of patient preference and pain was chosen based on previous studies that have shown decreasing topical medications increases patient satisfaction. Secondary endpoints including SPEED survey and corneal staining were chosen to test the hypothesis of less ocular surface disease with Dextenza. Time to epithelialization will be studied to see the positive or neutral effects of steroid plus punctal occlusion on epithelialization. Finally, the other secondary endpoints are standard measures for PRK.

The study inclusion and exclusion criteria were chosen based on patients who normally would be successful with laser refractive surgery. The study follow-up visits were based on the Vance Thompson Vision standard post-operative follow-up protocols.

2. STUDY ENDPOINTS

2.1 Primary Endpoint

To determine at Month 1 (Day 28 +/- 3 days):

- Patient preference as measured by adapted COMTOL survey at Month 1 following surgery.

2.2 Secondary Endpoints

To determine at Post-Operative Day 3 and 4:

- Percentage of eyes epithelialized at Day 3 and Day 4.

To determine through Month 1 (Day 28 +/- 3 days):

- Mean pain score per eye (Group A vs. Group B) as measured by the Numerical Rating Scale (NRS) at Day 3, Day 4, Week 2 (collected via telephone survey), and Month 1.
- Patient preference as measured by a modified SPEED questionnaire at Pre-op Visit and Month 1.

To determine through Month 3 (+/- 4 days):

- Incidence and grade of post-operative corneal haze as measured by Heidelberg Anterior Segment OCT at Pre-op Visit, Month 1, and Month 3.
- Post-operative corneal staining score as measured by the National Eye Institute (NEI) grading system at Day 3, Day 4, Month 1, and Month 3.

- Uncorrected visual acuity as measured by ETDRS chart at 4m at Month 1 and Month 3.
- Best-corrected visual acuity as measured by ETDRS chart at 4m at Month 1 and Month 3
- Manifest Refraction Spherical Equivalent as measured by the Optometrist at Month 1 and Month 3.

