Medical and Ocular History obtained: The site will ask and document all past Ocular history, relevant medical history and surgical history. A list of current medications, dose, route, start date and indications will be obtained and documented for each subject. There will be a subsequent diagnosis and start date for each medication.

[figure not shown]
BCDVA on ETDRS chart: (manifest refraction performed if vision is worse than 20/20 with current MRx). The BCDVA will be captured on an ETDRS worksheet and calculated

Slit Lamp Examination (SLE): Slit lamp examination will be performed on the study eye and fellow eye of each subject by a masked examiner, and will include assessment of the lids and lashes, conjunctiva, tear film, cornea, anterior chamber, iris, and lens. At the screening/Day 0 visit, and 30 day/exit visit SLE will be performed both prior to and following application of the ELM or Lipiflow.

Corneal Staining: A drop of fluorescein will be instilled on the eye, then the masked examiner will use the cobalt blue filter on the slit-lamp to examine the cornea. A grading scale of 0 to 3 is used to evaluate each of the five areas on the cornea. 0 being no staining to 3 being severe staining. All areas are then added together for a maximum score of 15.

National Eye Institute/Industry Grading System

Score each of 5 areas of the cornea and total score:

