5.2.2 Unscheduled Visits

All attempts should be made to keep patients on the study schedule. Unscheduled visits may be necessary to repeat testing following abnormal laboratory results, for follow-up of AEs, or for any other reason, as warranted.

If patient presents on POD 4 and have not epithelialized, patient will be brought in on POD 5 to re-assess epithelialization and remove bandage contact lens (BCL). This will be collected as an unscheduled visit.

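### Section 1.2.1 promises time to epithelialization, but Section 2.2 fixes only a yes/no percentage at Day 3 and Day 4, too coarse with 20 pairs to show moderate differences in healing speed

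*Protocol*

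**What the plan says.** Section 1.2.1 (Rationale for Study Design) sets the aim: "Time to epithelialization will be studied to see the positive or neutral effects of steroid plus punctal occlusion on epithelialization". Section 1.1 makes better epithelialization part of the case for the insert.

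Section 2.2 turns this aim into "Percentage of eyes epithelialized at Day 3 and Day 4". The synopsis endpoint list has "Percentage of eyes epithelialized at POD 4", with no Day 3.

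The comparison is within patient. The synopsis says "The first eye will be randomized to Group A or B; the second eye will be selected for the opposite group", with 20 patients and 40 eyes.

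Three other provisions bear on the point:

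- **Slit-lamp exam.** Both eyes are examined at Day 3 and Day 4. Section 5.2.1 says "Slit lamp examination will be performed on the study eye and fellow eye of each subject by a masked examiner".
- **POD 5.** Under Section 5.2.2, a patient who is not epithelialized on POD 4 is re-assessed on POD 5, recorded as an unscheduled visit.
- **Staining.** A graded corneal staining score is taken at the same two visits: "A grading scale of 0 to 3 is used to evaluate each of the five areas on the cornea", with a maximum of 15. Section 1.2.1 links staining to ocular surface disease, not to wound closure.

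Neither Table 1 nor the Visit 3 and Visit 4 lists has a line for epithelial status, day of healing or defect size.

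**The concern.** The stated aim is about speed, but the endpoint is a snapshot. On a given day each eye is scored healed or not healed, and a paired comparison then draws only on patients whose two eyes differ. A patient with a pinpoint defect in one eye and a large one in the other counts as no difference.

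Section 1.2.1 names a neutral effect as one of the results of interest. An insensitive endpoint tends to look neutral whether the insert speeds healing, slows it or does nothing. An analysis plan can choose a better test, but it cannot recover a measurement that was never taken.

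**Working it through.** The protocol gives no power, alpha or expected healing rate for this endpoint, so there is no figure to reproduce. A two-sided 0.05 level and no dropout are assumed throughout.

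**1. What a single-day yes/no comparison needs.** Input: 20 pairs (synopsis). For an exact McNemar test with n discordant patients, of whom k go the minority way, p = 2 × P(X ≤ k), X ~ Binomial(n, ½).

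- 5-0: 2 × (1/32) = 0.0625
- 6-0: 2 × (1/64) = 0.031
- 7-1: 2 × (1 + 8)/256 = 0.070
- 8-1: 2 × (1 + 9)/512 = 0.039

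The smallest significant result is therefore 6-0. With 6, 7 or 8 discordant patients, all must go one way; a single reversal is tolerated only from 9 upward. No healing assumption enters here.

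Example: 70% against 50% healed, eyes independent. Expected discordant counts are 20 × 0.7 × 0.5 = 7 and 20 × 0.3 × 0.5 = 3. A 7-3 split gives p = 2 × (1 + 10 + 45 + 120)/1024 = 0.34.

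**2. Power by size of difference.** Full enumeration, 20 pairs, between-eye correlation assumed 0 to 0.7:

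| Healed, one group vs the other | Power |
|---|---|
| 95% vs 80% | 8-9% |
| 70% vs 50% | 15-20% |
| 90% vs 70% | 19-20% |
| 75% vs 50% | 24-34% |
| 80% vs 50% | 37-52% |
| 80% vs 40% | 62-83% |

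Differences of 15 to 25 points are missed more often than found, 30 points is about a coin toss, and 40 points is usually found.

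**3. Alternatives at the same visits.** Assumed, not in the protocol: closure time normal with mean 2.8, 3.0 or 3.5 days, SD 0.7 day, between-eye correlation 0.5, true shift 0.4 day either way, and defect diameter proportional to remaining healing time.

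Why one day can be uninformative: at mean 3.5 and shift +0.4, the shares healed at Day 3 are Φ((3 − 3.5)/0.7) = 24% and Φ((3 − 3.9)/0.7) = 10%. Power is 7% on Day 3 and 21% on Day 4.

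Signed-rank tests on ordered healing day (by Day 3, by Day 4, by POD 5, later) and on Day 3 diameter without measurement error, 1,000 runs each (simulation SE up to √(0.5 × 0.5/1000) = 1.6 points):

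| Mean / shift (days) | Ordered healing day | Day 3 diameter |
|---|---|---|
| 3.5 / +0.4 | 48% | 61% |
| 3.5 / −0.4 | 48% | 53% |
| 3.0 / +0.4 | 50% | 54% |
| 3.0 / −0.4 | 39% | 39% |
| 2.8 / +0.4 | 40% | 46% |
| 2.8 / −0.4 | 34% | 32% |

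Repeat runs move these by a few points. Ranges over the six scenarios, repeats included:

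- Day 3 yes/no: 6-24%
- Ordered healing day: 32-50%
- Day 3 diameter: 32-63% without error, 32-54% with modest error (assumed SD equivalent to 0.25 day)
- Paired t-test on defect area: 14-50%

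With no true effect, the McNemar test rejects in at most 1.4% of runs and the ordered-day test in 3-5%. Part of the gain is therefore escape from a conservative test.

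**4. Wider grid.** Over 96 scenarios (mean 2.5-4.0 days, SD 0.5-1.0, correlation 0.3-0.6, shift 0.4-0.7 SD), median power is 12% for yes/no on the better day and 37% for Day 3 defect size by signed-rank test. The median ratio is 2.2 (range 1.3-9.5). Against a three-level ordering tested by a sign test, it is 1.6 (1.1-2.8). At the larger shift, the ratio against yes/no falls to about 1.3-1.5 when about three quarters of eyes are healed by Day 3.

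**The case against.** This is one of several secondary endpoints, the protocol claims no power for it, and no figure is wrong. Complete closure is meaningful in its own right: failure to close by POD 4 triggers the POD 5 visit. The choice of test belongs to the analysis plan, which is not shown. All of this stands, and it limits the priority.

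Healing is also not wholly reduced to one yes/no. Two days plus POD 5 give ordered levels, and the staining score is graded at the same exams. That stands too, although no endpoint uses the ordering, and the staining score is not defined as defect size.

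A reader might infer from the wider grid that measuring defect size would by itself roughly double the power. The documents do not support that. Every healing input is assumed, and the ratio of 2.2 is against single-day yes/no. In the six scenarios of step 3, ordered healing day recovers most of the gain without a new measurement. The benefit also depends on the analysis, since a t-test on area can do no better than yes/no. And defect size alone does not give the promised time to healing.

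Feasibility is partly open. Section 5.2.2 implies that a bandage contact lens is still on unhealed eyes at POD 4, and the protocol does not say how a defect is viewed through or around it. The same question applies to the healed/not-healed judgement that the protocol already needs.

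**Conclusion.** The point holds as a mismatch between aim and endpoint, with a loss of sensitivity as the consequence. Section 1.2.1 promises time, Section 2.2 gives a percentage on two days, and the synopsis gives one day.

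The 6-0 threshold follows from 20 pairs and a two-sided 0.05 level. The power figures do not come from the protocol. They rest on the assumed healing times, SD, correlation and a 0.4-day shift, under which moderate differences in healing speed would mostly be missed by single-day yes/no. Ordered healing day raises power clearly. Defect diameter adds between nothing and a modest further amount, depending on measurement error and on how many eyes are still open at Day 3.

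Priority is low to moderate. The change is worth making because it is cheap and delivers the stated aim.

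**What to change.** 1. Keep the percentage healed, and align the synopsis with the Day 3 and Day 4 endpoint in Section 2.2.
2. Add to Section 2.2 a secondary endpoint: ordered day of healing per eye (by Day 3, by Day 4, by the POD 5 re-assessment, later), compared within patient by a rank-based paired test.
3. Add a line for epithelial status per eye to Table 1 and to the Visit 3 and Visit 4 lists, and carry the POD 5 finding into the same variable.
4. Record residual epithelial defect size per eye (longest diameter in mm, 0 if closed) at the Day 3 and Day 4 slit-lamp exams. Compare it by the same rank-based test, not by a t-test on area.
5. State how epithelial status and defect size are viewed with the bandage lens in place.

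Cost: a few lines of text and one extra CRF field for the diameter, at exams already scheduled. Items 1 to 3 need no new measurement. Item 4 brings some measurement error, and its practicality depends on the answer to item 5.
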